Cognition development. In Project Viva, the child's cognition development, including intelligence, visual-motor, and memory-learning, was measured at 3 y and 7 y of age⁵⁰. For the intelligence domain, trained research staff administered the Peabody Picture Vocabulary Test-3rd edition (PPVT-III, a test of receptive language) at 3 y of age, and the Kaufman Brief Intelligence Test-2nd edition (KBIT-II, verbal and non-verbal intelligence) at 7 y of age. For the visual-motor domain, research staff administered the Wide Range Assessment of Visual Motor Abilities (WRAVMA) at the 3-y visit. WRAVMA includes the fine motor (pegboard), visual spatial (matching), and visual motor (drawing) subtests. Subtest scores were combined to yield the total WRAVMA score. At the 7-y visit, staff administered the WRAVMA visual motor (drawing) subtest only. For the memory-learning domain, staff administered the design memory and picture memory subsets of Wide Range Assessment of Memory and Learning (WRAML) at the 7-y visit. These two subset scores were combined to yield the total WRAML score.

Effect modifier. We are interested in effect modification by child sex (Boys vs Girls).

Confounders. Potential confounders include family income; health history of family members; parental education attainment, employment, and preconception BMI; and maternal intelligence, age, race/ethnicity, marital status, parity, pregnancy complications, prenatal vitamins, smoking, and delivery method; early mode of infant feeding including breastfeeding duration and exclusivity. We will also adjust for child actual age at assessments.

Data analysis. All our analyses will be first conducted among boys and girls separately to examine the potential sex differences (if significant, sex-stratified results will be reported).

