For **Aim 1 (infant age of egg introduction)**, we will first classify the infants based on their age of egg introduction: never, <2 m, 2-3 m, 4-5 m, 6-8 m, 9-11 m, and 12 m. Then we will compare their physical growth, obesity, cardio-metabolic risk profile, risk of food allergy, and cognition test scores in mid-childhood and adolescence using Chi-square tests (categorical outcomes) or ANOVA tests (continuous outcomes). We will fit multivariable linear (continuous outcomes) or logistic (binary outcomes) regression models with fractional polynomial functions of infant age of egg introduction, adjusted for significant confounders. Both linear (e.g., earlier introduction, high probability of the outcome) and non-linear (e.g., threshold effect) associations will be tested. The non-linear trend will be examined through visualization of scatter plots and statistical tests of polynomial term of infant age of egg introduction in the regression models. If the polynomial terms of age are not significant, we will drop it and consider the association to be linear.

Then, we will fit a mixed effect model (SAS PROC MIXED) for continuous outcomes (height z-score and BMI z-score) and a generalized linear mixed effect model (SAS PROC GLIMMIX) for binary outcomes (obesity and diagnosis of food allergy) that were measured repeatedly across multiple age points. The mixed effect model will include random intercepts, random slopes for age effects, and autoregressive variance-covariance matrix across different time points. Independent variables in the model will include infant age of egg introduction, outcome age point (mid-childhood and adolescence), the 2-way interaction term (infant age of

egg introduction × outcome age point), and significant covariates. The 2-way interaction term quantifies the extent to which infant age of egg introduction can affect the specific outcome. The PI has experience with using mixed effect models for examine child growth measures and multiple publications in this area.^{51,52}

For **Aim 2 (frequency of infant egg intake)**, we will first classify the infants based on their frequency of egg intake: never, <once/week, once/week, 2–4 times/week, nearly daily or daily, and ≥ 2 times/day. Then, we will use similar analytic methods mentioned above for Aim 1 to compare their health and developmental outcomes.

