In addition, we will create an **average probability of multiple child outcomes** to balance across different aspects of child health and development using the methods published by Oken et al.⁵³ for identifying the lowest-risk exposure level when multiple outcomes are considered. Specifically, we will focus on 6 binary child outcomes including stunting, underweight, obesity, high risk of metabolic syndrome (e.g., z score $\geq 95^{\text{th}}$ percentile), food allergy, and cognitive delay (e.g., standardized cognition score < 85 points). We will use estimates from aforementioned logistic models to generate predicted probabilities of each of the 6 adverse outcomes when the independent variable of infant egg consumption (i.e., age of egg introduction or frequency of egg intake) varies across the observed range within our study sample. We will calculate the average probability of the 6 outcomes, assuming these outcomes are equally important. We will identify the lowest-risk infant egg consumption when the corresponding average probability of the 6 adverse outcomes is the lowest.

We will handle missing data with Multiple Imputation.⁵⁴ Specifically, we will first generate 20 replicates of datasets (PROC MI in SAS) with imputed values for missing data on infant egg consumption, child outcomes, and significant covariates, based on a bayesian approach. The 2nd stage is to use standard statistical methods (e.g., Linear Regression) to fit the model of interest to examine the association between infant egg consumption and the specific outcome within each of the 20 imputed datasets. The 3rd stage is to pool the analytic results from all 20 imputed datasets to get the average estimates of the association (PROC MIANALYZE). The PI has experience with Multiple Imputation for large datasets.⁵⁵

All our analyses will be first conducted among boys and girls separately to examine the potential sex differences. A formal interaction test will be conducted by including the interaction term of egg consumption and sex into the regression models. If the interaction term is significant, sex-stratified results will be reported. Otherwise, sex-pooled analytic results will be reported.

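### Child sex is not in the adjustment set of the default sex-pooled linear models, so outcomes that are not sex-standardised may be analysed with avoidable residual variance; this is a precision cost, not a bias

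*Combined protocol and SAP*

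**What the plan says.** All references are to the Combined protocol and SAP, section 3) Project Design.

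- *Effect modifier* names child sex, boys against girls, and gives it no other role.
- *Confounders* begins "Potential confounders include family income; health history of family members; parental education attainment, employment, and preconception BMI", continues through maternal characteristics and infant feeding, and ends "We will also adjust for child actual age at assessments". Child sex does not appear.
- *Data analysis*, Aim 1: the linear and logistic models are "adjusted for significant confounders". For the mixed models, "Independent variables in the model will include infant age of egg introduction, outcome age point (mid-childhood and adolescence), the 2-way interaction term" and significant covariates; no sex term is named. Aim 2 follows similar methods.
- *Data analysis*, closing paragraph: analyses are first run in boys and girls separately, then "A formal interaction test will be conducted by including the interaction term of egg consumption and sex into the regression models". A significant interaction leads to stratified reporting. "Otherwise, sex-pooled analytic results will be reported".
- *Obesity* and *Cardio-metabolic health*: BMI categories and the components of the metabolic syndrome z score are sex-specific. No sex standardisation is described for fat, lean and trunk fat mass indices, skinfolds, blood pressure, lipids, glucose, insulin, HOMA-IR, adiponectin or CRP as separate outcomes, nor for waist under *Physical growth*.

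**The concern.** The plan removes sex differences from some outcomes by construction but leaves them in the raw measures, where it adjusts for age and not for sex. A covariate that predicts the outcome but is unrelated to the exposure is not a confounder, so a rule that admits only significant confounders does not ensure that it enters, however well it predicts.

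Pooled results are the default report. In those linear models any boy-girl difference left in the residual widens the interval around the egg effect. Sex must already be available for the stratified analyses, so the loss is avoidable. At stake is the width of intervals for the body-composition and cardio-metabolic measures, all of them from Project Viva.

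**Working it through.** **1. The plan's own figure.** *Statistical Power* gives detectable effect sizes for continuous outcomes of 0.054 (Project Viva, N = 2,128) and 0.051 (IFPS II, N = 3,033), with type 1 error 0.05 and power 0.8. Neither the metric nor the sidedness is stated. Read as a correlation, r = tanh[(z_alpha + z_power)/√(N − 3)]:

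| Cohort | Stated | Two-sided | One-sided |
|---|---|---|---|
| Project Viva | 0.054 | tanh(2.802/√2125) = 0.0607 | tanh(2.486/√2125) = 0.0539 |
| IFPS II | 0.051 | tanh(2.802/√3030) = 0.0509 | tanh(2.486/√3030) = 0.0451 |

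Each figure is matched by one convention, but no single convention tried gives both. The point here does not depend on this: the gain below is proportional and holds at any N. The figure 0.054 serves only as an illustration. It uses the full cohort, and the documents do not give the number of children with each later measurement.

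**2. Inputs for the gain.** The documents report no sex difference for any outcome. So d, the boy-girl mean difference in within-sex SD units (after the other covariates), is an assumption shown over a range. Two further assumptions are an even sex split and no association between sex and egg exposure.

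**3. Formulas.** With an even split, the difference adds d²/4 to a within-sex variance of 1:

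- R² = (d²/4)/(1 + d²/4)
- SE adjusted / SE unadjusted = √(1 − R²)
- equivalent gain in sample size = 1/(1 − R²) − 1 = d²/4
- power with sex, where it is 80% without = Φ(2.802/√(1 − R²) − 1.960), two-sided 5%

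For d = 0.5: d²/4 = 0.0625; R² = 0.0625/1.0625 = 0.0588; SE ratio = √0.9412 = 0.970.

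**4. Results.**

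| Assumed d (SD) | R² | SE ratio | Equivalent extra children | Power, from 80% | 0.054 becomes |
|---|---|---|---|---|---|
| 0.1 | 0.0025 | 0.999 | 0.25% | 80.1% | 0.0539 |
| 0.2 | 0.0099 | 0.995 | 1% | 80.4% | 0.0537 |
| 0.3 | 0.0220 | 0.989 | 2.25% | 80.9% | 0.0534 |
| 0.5 | 0.0588 | 0.970 | 6.25% | 82.3% | 0.0524 |
| 0.8 | 0.1379 | 0.929 | 16% | 85.5% | 0.0501 |
| 1.0 | 0.2000 | 0.894 | 25% | 87.9% | 0.0483 |

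**5. Where it applies.** The formula is for linear models. The mixed models are specified for height z, BMI z, obesity and food allergy. The first two are referred to growth standards, obesity rests on sex-specific BMI, and food allergy is binary. The metabolic syndrome z score is sex-specific by construction. What remains is the set of pooled linear models for the raw measures listed above.

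**The case against.** The best defence is that the plan is silent on sex adjustment and does not exclude it. The confounder list is worded as open-ended, sex has its own paragraph, stratified analyses come first, and an interaction test is planned. If significance is judged against the outcome, an analyst who added sex as a candidate would keep it exactly where it matters most. All of this is fair. It shows that sex was not overlooked, but it does not put sex into the pooled models: sex is not a listed candidate, and the rule for entry is not one that a prognostic non-confounder need pass.

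The defence is also right about size. The documents support no particular sex difference, one range cannot describe blood pressure, lipids and DXA measures alike, and small differences yield almost nothing.

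A reader might infer three stronger things, none of which the documents support:

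- *That the pooled estimates are biased.* Nothing in the documents links sex to egg introduction or frequency. Without such a link the linear estimate is not shifted; it only carries more noise.
- *That every model gains.* In logistic regression, adding a prognostic covariate unrelated to exposure does not shrink the standard error of the log odds ratio; it tends to raise it slightly and moves the estimate to a conditional one. The average probability of six adverse outcomes, on which Hypotheses 2 and 3 rest, is built from logistic models, so no gain is claimed there.
- *That the interaction test is run without a sex main effect and is therefore invalid.* The text names only the product term, but that is ordinary shorthand, and nothing says the main effect is dropped. A confirmation is worth asking for, because without the main effect the product term would absorb part of any boy-girl mean difference, and this test decides what is reported.

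**Conclusion.** The point holds for the sex-pooled linear models of outcomes that are not sex-standardised. Followed as written, the plan may leave sex differences in the residual of those models. The loss is negligible for differences up to about 0.3 SD, about 3% of the standard error at 0.5 SD, and about 11% at 1.0 SD. These sizes rest on assumed differences, an even sex split, and independence of sex and egg exposure. No stated figure is overturned and no conclusion is shown to be wrong. It is a modest improvement worth making because it costs almost nothing.

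**What to change.** Add to *Confounders* or *Data analysis* that child sex is a fixed covariate, whatever its p-value, in the sex-pooled linear models of fat, lean and trunk fat mass indices, skinfolds, waist, systolic and diastolic blood pressure, lipids, insulin, HOMA-IR and the other raw biomarkers. Add a sex-by-age term only if such an outcome is modelled across ages. State also that the sex main effect is kept in every egg-by-sex interaction model.

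The cost is a sentence or two of text and one degree of freedom per model (more where sex-by-age is added). No new data are needed.

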We propose a 2-year study to examine how infant egg consumption (age of introduction and frequency of intake) influences physical growth, obesity, cardio-metabolic health, risk of food allergy, and cognition development in mid-childhood and adolescence. We will use existing data from two US longitudinal birth cohorts that tracked mother-child dyads from pregnancy to adolescence: 1) Project Viva (1999-present) that enrolled 2,341 pregnancies and followed children at delivery, 6 months (m), then yearly from 1 year (y) to 15 y of child age, and 2) the Infant Feeding Practices Study II (IFPS II, 2005-2007) that enrolled 3,033 pregnancies with surveys in late pregnancy, neonatal (1 m), then monthly from 2 m to 12 m of infant age, and at 6 y. For **Aim 1**, we will classify infants based on their age of egg introduction: never, <2 m, 2-3 m, 4-5 m, 6-8 m, 9-11 m, and ≥ 12 m. We will compare physical growth, obesity, cardio-metabolic health, food allergy, and cognition test scores in mid-childhood and adolescence. We will fit multivariable linear or logistic regression models with fractional polynomial functions of infant age of egg introduction. Both linear (e.g., earlier introduction, higher probability of the outcome) and non-linear (e.g., threshold effect) associations will be tested. For **Aim 2**, we will classify infants based on their frequency of egg intake: never, <once/week, once/week, 2-4 times/week, nearly daily or daily, and ≥ 2 times/day. We will use similar analytic methods mentioned above to compare their later outcomes. Finally, we will create an average probability of multiple child outcomes to balance across different aspects of child health and development. We will identify the lowest-risk infant egg consumption when the corresponding average predicted probability of the related adverse outcomes is the lowest.

Section 2: Detailed Research Plan

1) Background Information:

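### A fractional polynomial in age alone cannot represent infants with no egg introduction recorded by 12 m; they need their own term in the adjusted Aim 1 models.

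*Combined protocol and SAP*

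**What the plan says.** In the combined protocol and SAP, section 3) Project Design, Data analysis (Aim 1), infants are grouped by "age of egg introduction: never, <2 m, 2-3 m, 4-5 m, 6-8 m, 9-11 m, and 12 m" for chi-square and ANOVA comparisons. The opening summary gives the same list with a different last class: "never, <2 m, 2-3 m, 4-5 m, 6-8 m, 9-11 m, and ≥ 12 m". The Statistical Power paragraph also uses ≥ 12 m, in its example contrast with 6-8 m.

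The adjusted analysis is different in kind. It consists of linear and logistic "regression models with fractional polynomial functions of infant age of egg introduction". The fallback is: "If the polynomial terms of age are not significant, we will drop it and consider the association to be linear". The lowest-risk step rests on these models: "We will use estimates from aforementioned logistic models to generate predicted probabilities of each of the 6 adverse outcomes", as the exposure "varies across the observed range within our study sample", and then "We will identify the lowest-risk infant egg consumption when the corresponding average probability of the 6 adverse outcomes is the lowest".

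Under Age of egg introduction, Project Viva asked the age at 6 m and 12 m, and IFPS II derives it from surveys between 2 and 12 m that ask about the past 7 days. The same paragraph gives 1.7% of IFPS II infants introduced by 6 m and 63.0% by 12 m. Multiple imputation covers "imputed values for missing data on infant egg consumption, child outcomes, and significant covariates".

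No section says how an infant without egg by 12 m enters the polynomial models.

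**The concern.** A fractional polynomial needs a number for every infant. An infant with no introduction by 12 m has none, and 'never' is a class, not a point on the age scale. Someone fitting the model as written must drop these infants, give them a number, or let the imputation give them one. Each of these is worse than a separate term.

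The choice matters because Hypothesis 2 places the optimum between 6 and 12 months, next to this group. The lowest-risk step also takes the minimum of the fitted curve without a test or interval. Delayed against earlier introduction is a central Aim 1 question, and it is the contrast that the power paragraph uses as its example. If the group is dropped, that contrast survives only in the unadjusted comparisons.

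**Working it through.** **1. Size of the group.** IFPS II: 100 − 63.0 = 37.0% not introduced by 12 m. Applied to all 3,033 newborns, 0.37 × 3,033 ≈ 1,122 infants without an age and 0.63 × 3,033 ≈ 1,911 with one. The percentages come from an earlier analysis whose denominator is not stated, so the counts are approximate. No share is given for Project Viva.

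**2. The plan's own design figures.** Statistical Power gives detectable odds ratios of 1.46 (N=2,128) and 1.38 (N=3,033). A two-sided two-proportion calculation with a 1:1 split of the full cohort and 10% baseline risk gives 1.458 and 1.376. The split and baseline risk are assumed, since the plan gives neither. On the same assumptions, 1,911 infants instead of 3,033 would raise the IFPS II figure to about 1.49. The point below does not depend on this.

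**3. The possible routes.**

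| Route | Effect |
|---|---|
| Drop the group | Curve over known ages is unaffected by them; adjusted contrast of delayed with earlier introduction is lost |
| Code as 12 m | Their risk difference is absorbed into the age slope |
| Impute an age | Could assign an age before 12 m, against the record |
| Own indicator, polynomial over recorded ages | Curve and contrast are both kept |

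**4. Coding as 12 m, worked through.** Assumed: 6% risk at every known age and 9% in the group; full N, no loss to follow-up, no confounders. Of the infants with a known age, a fraction 1.7/63 is spread over 3, 5 and 6 m and the rest evenly over 7-12 m. The model is logit(p) = b0 + b1 × age, fitted to expected counts.

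- IFPS II, share 37%: odds ratio per month 1.081, z 2.01, although risk is flat over known ages.
- Project Viva, assumed shares 10/20/37/50%, with the same IFPS II-based age pattern: 1.033/1.056/1.081/1.094, z 0.69/1.19/1.69/1.85.
- IFPS II with other risks in the group: 8% gives 1.055 (z 1.38), 7% gives 1.028 (z 0.71), 4% gives 0.940 (z −1.55).
- With an indicator instead, the age odds ratio is 1.00 and the group's odds ratio against known ages is (0.09/0.91)/(0.06/0.94) = 0.0989/0.0638 = 1.55, which is what was put in.
- The best two-term fractional polynomial (powers 3, 3) has its minimum at about 8.5 m. In IFPS II its fitted risks are 7.6% at 3 m, 5.7% at 8.5 m and 8.3% at 12 m. Its likelihood-ratio gain over the line is only 1.59 in IFPS II and 0.34 to 1.12 in Project Viva. The fallback rule would therefore usually return a line, whose minimum is at an end of the range.

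**5. How often the chosen age changes.** These are one-outcome simulations at Project Viva's size, with shares of 10 to 50% assumed, the IFPS II-based age pattern, and the fallback rule read as a 3-df test at 0.05. Coding as 12 m and using known ages only gave answers more than 1 m apart in about 25 to 49% of datasets at 6% against 9%. With no risk difference at all they still differed in about 13 to 24%.

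**The case against.** The strongest reply is that 'never' plainly has no age, so these infants fall outside the polynomial, and predictions are already confined to the observed range. No section proposes coding them as 12 m, and a class listed as observed is not obviously missing data. On that reading the curve over known ages is sound, and without covariates the indicator gives exactly the same curve. This stands: the gain over dropping the group is then the retained adjusted contrast, not a better curve. It does not remove the point, because the plan does not state that reading and the contrast would still be lost.

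A reader might go further and infer that the coding decides the reported lowest-risk age. The documents do not support that. About half of the simulated disagreement remains when there is no risk difference, so it comes from taking a minimum on flat data. The simulation covers one outcome, whereas the plan averages six. The metabolic and cognition outcomes are described only for Project Viva, whose share is unknown, so the 37% cannot be carried to the six-outcome curve.

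Three further limits stand. IFPS II status rests on 7-day recall, and the Sample/Data list has no survey at 8 or 11 m, so calling these infants known to be unexposed is too strong. The difference between '12 m' and '≥ 12 m' may be a symbol lost in text extraction. The lowest-risk step cites a published method that could not be consulted here.

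**Conclusion.** The point holds as a weakness in the adjusted Aim 1 models and should be fixed. A polynomial in age alone cannot represent about 37% of IFPS II infants and an unstated share of Project Viva, and a separate indicator is better than any way of fitting the model as written. The distortion from coding as 12 m is an odds ratio of about 1.08 per month in IFPS II. It rests on the assumed 6% and 9% risks and shrinks or reverses with other risks.

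The point does not reach the chi-square and ANOVA comparisons, which can use 'never'. It reaches the mixed models only if age is continuous there, which the plan does not say. It is not a finding that the reported optimum will be wrong.

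**What to change.** 1. Keep these infants in the adjusted linear and logistic models with their own indicator (no introduction recorded by 12 m), and fit the fractional polynomial over infants with a recorded age. Do the same in the mixed models if age enters as continuous.
2. Do not impute an introduction age before 12 m for infants whose records through 12 m show no egg. Impute only where status or age is missing, and note that the IFPS II status rests on 7-day recall.
3. In the lowest-risk step, report this group's predicted average probability beside the curve, and claim an optimum only within the recorded ages.
4. Use one label for the top class throughout. Project Viva's later surveys offer 'never' for whole eggs in the past month; where those answers allow, 'never' may stay separate from later introduction.
5. If simulated changes in the chosen age are used to support a coding choice, show them beside the no-difference case and label them as one-outcome illustrations.

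The cost is plan wording and recoding, with no new data. The downside is that the curve's shape rests on fewer infants (about 1,911 of 3,033 in IFPS II; the Project Viva count is not given), and no optimum beyond 12 m can be claimed.

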supports their potential influences on child health and development⁴³. We recognize that other aspects of infant egg consumption such as different egg fractions (i.e., white vs yolk⁴⁴) may also influence child outcomes but they were not collected in Project Viva or IFPS II.

Age of egg introduction. At **Project Viva** visits, the age of infant egg introduction was asked at 6-m and 12-m using the same question - “How old was your baby when you first fed him/her eggs”. In the **IFPS II**, mothers reported their infant’s intake of 18 types of foods in the past 7 days through monthly surveys from 2-12 m of infant ages. The question used for infant food intake was - “In the past 7 days, how often was your baby fed each food listed below? Include feedings by everyone who feeds the baby and include snacks and night-time feedings.” “Eggs” were one of the 18 types of foods. Accordingly, we will derive the infant age of egg introduction from IFPS II mothers’ monthly responses to infant egg consumption. Our previous analysis on infant dietary patterns showed that 1.7% and 63.0% of IFPS II infants had been introduced eggs by 6 m and 12 m of age, respectively⁴².

Frequency of egg intake. At the 2-y survey in **Project Viva**, the frequency of infant egg intake in the past month was obtained from the mothers’ response to the question - “Please check the box that best represents how often your child eats each of the foods listed, on average, in the past month”. One of the food items for this question was “Whole eggs”. Response options for the frequency of consuming “Whole eggs” included “never”, “<once/week”, “once/week”, “2–4 times/week”, “nearly daily or daily”, and “≥2 times/day”.

The same question was asked again at surveys at 3 y and 7 y. As mentioned above, mothers in the IFPS II reported their infant's intake of eggs in the past 7 days through the monthly surveys from 2-12 m of infant ages. Infant egg intake was reported as the number of feedings per day or per week. Our analysis on infant dietary patterns showed the mean egg intake among IFPS II infants was 0.01 (SD, 0.10) and 0.27 (SD, 0.37) serving/week at 6 m and 12 m, respectively⁴².

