Child outcome measures. We will focus on child physical growth, obesity, cardio-metabolic health, risk of food allergy, and cognition development (**Figure 1**). These child outcomes were chosen because they 1) may be influenced by infant egg consumption (see '**Background**'), 2) are clinically important, and 3) were measured in Project Viva and/or IFPS II.

Physical growth. In Project Viva, birth weight was obtained from birth certificates. Research staff measured children's length/height, weight, and waist circumference at 6 m (infancy), 3 y (early childhood), 7 y (mid-childhood), 12-13 y (early teen), and 14-15 (mid-teen)^{37,45}. Additional data on child weight and length/height were obtained from medical records at well-child visits. In IFPS II, mothers reported infant birth weight and length in neonatal survey; weight, length, and age at their most recent doctor's visit in 3-m, 5-m, and 7-m, 12-m, and 6-y surveys^{38,42}. Body mass index (BMI) was calculated as, weight in kg/(height in meters)². We will define stunting as height-for-age z score < -2, and underweight as sex- and age-specific BMI < 5th percentile according to World Health Organization (WHO) Growth Standards^{46,47}.

Obesity. In both Project Viva and IFPS II, we will define child obesity as sex- and age-specific BMI \geq 95th percentile according to WHO Growth Standards^{46,47}. In Project Viva, skinfold thickness was measured at 3 y, 7 y, 12-13 y, and 14-15 y. In addition, fat, lean and trunk fat mass were measured through whole-body dual X-ray absorptiometry (DXA) scans performed at 7 y, 12-13 y, and 14-15 y. Accordingly, we will calculate fat mass index (FMI, kg/m²), lean mass index (LMI, kg/m²), and trunk fat mass index (TFMI, kg/m²).

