Statistical Power. We expect sufficient statistical power for our hypothesis-driven data analyses for both Aims, because 1) the 2 cohorts had relatively large sample sizes (N=2,128 for Project Viva and N=3,033 for IFPS II), which are sufficient to detect a small odds ratio (1.46 for Project Viva, 1.38 for IFPS II with type 1 error being 0.05 and power being 0.8) of binary child outcomes (e.g., food allergy) between infants with different egg consumption (e.g., egg introduced at ≥ 12 m vs 6-8 m) or a small effect (effect size=0.054 for Project Viva, 0.051 for IFPS II) of infant egg consumption on continuous outcomes (e.g., intelligence score); 2) most child outcomes were measured repeatedly; 3) infant egg consumption varied largely within cohorts.

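### IFPS II: the seven-category chi-square tests have expected counts below 1 for rarer outcomes and no sparse-cell rule, so their p-values are likely too small; the effect is confined to the unadjusted first comparisons

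*Combined protocol and SAP*

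**What the plan says.** Under Project Design, Data analysis, Aim 1, infants are classified by age of egg introduction as "never, <2 m, 2-3 m, 4-5 m, 6-8 m, 9-11 m, and 12 m". Their outcomes are then compared "using Chi-square tests (categorical outcomes) or ANOVA tests (continuous outcomes". No exact p-value, minimum expected count or merging rule is given. Adjusted fractional-polynomial regressions and mixed models follow, and Aim 2 uses similar methods for frequency of intake.

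Under Age of egg introduction, the plan reports that "1.7% and 63.0% of IFPS II infants had been introduced eggs by 6 m and 12 m of age, respectively". It derives the IFPS II introduction age from maternal reports "through monthly surveys from 2-12 m of infant ages". The cohort sizes, under Statistical Power, are "N=2,128 for Project Viva and N=3,033 for IFPS II". On sex, the Data analysis text says: "All our analyses will be first conducted among boys and girls separately to examine the potential sex differences".

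**The concern.** The Pearson chi-square p-value is a large-sample approximation that fails when cells expect less than about one event. The plan's own IFPS II figures put very few infants into three of the seven categories, and the sex-specific runs halve those again. One chance event in a tiny category can then carry the whole test.

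The excess false signals would come from infants introduced to eggs before 6 months. That group bears directly on the early-introduction question raised in the Background, and a very small p-value there would be easy to over-read.

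**Working it through.** **The plan's own figure.** The only error-rate statement is the detectable odds ratio: "1.46 for Project Viva, 1.38 for IFPS II with type 1 error being 0.05 and power being 0.8". With an assumed 10% baseline risk, 1:1 groups and two-sided 0.05, power comes out at 0.803 for 1.46 and 0.808 for 1.38. The figures are therefore reproducible under those assumptions, but they describe a two-group contrast and say nothing about a seven-category table.

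**Inputs from the documents.** IFPS II N = 3,033; 1.7% introduced by 6 months; 63.0% by 12 months; seven categories, hence 6 degrees of freedom against a binary outcome.

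**Assumed inputs.**
- The 1.7% applies to all 3,033 infants, and the sexes are equal in number.
- Outcome rates are nominal reference values: 2.3% for "stunting as height-for-age z score < -2" and 5% for the underweight cut-off at the 5th percentile. Observed IFPS II rates are not given.
- The split of the early infants over <2, 2-3 and 4-5 months is not given, so it is varied.

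**Step 1: expected counts.** Early infants: 3,033 × 0.017 = 51.6, about 52 (about 26 per sex). If all three early categories are populated, the smallest holds at most 51.6 / 3 = 17.2 infants, or 8.6 per sex. Its expected events are at most:

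| Outcome rate | Full N | One sex |
|---|---|---|
| 2.3% | 17.2 × 0.023 = 0.40 | 0.20 |
| 5% | 17.2 × 0.05 = 0.86 | 0.43 |
| 10% | 17.2 × 0.10 = 1.72 | 0.86 |

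The smallest cell must fall below 1 for any outcome rarer than 1 / 17.2 = 5.8% at full N, or 1 / 8.6 = 11.6% within one sex.

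**Step 2: mechanism.** Take a cell of 3 infants at 2.3%, so the expected count is 0.069. One event contributes (1 − 0.069)² / (0.069 × 0.977) = 12.9. The 5% critical value on 6 df is 12.59, so a single child makes the overall test significant.

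**Step 3: size of the test.** Null tables were simulated with fixed category sizes (200,000 or more per scenario). At full N the later categories were 1,122 not introduced by 12 months and an assumed 600, 900 and 359 for the other three. Each entry gives rejection at nominal 5%, then how many times too often p<0.001 occurs.

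| Early infants (<2 / 2-3 / 4-5 m) | Rate 2.3% | Rate 5% | Rate 10% |
|---|---|---|---|
| 3 / 10 / 39 | 10.6%, 13× | 6.3%, 10× | 6.5%, 4× |
| 5 / 10 / 37 | 8.0%, 11× | 6.7%, 6× | 5.6%, 3× |
| 17 / 17 / 18 | 6.6%, 10× | 5.9%, 5× | 5.3%, 2× |
| 0 / 5 / 47 | 7.4%, 8× | 5.9%, 5× | 5.3%, 3× |
| 0 / 26 / 26 | 6.1%, 6× | 5.4%, 3× | 5.1%, 2× |
| 0 / 0 / 52 | 5.2%, 2× | 5.0%, 2× | 5.0%, 1× |

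Two other layouts of the later categories gave nearly the same results.

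**Step 4: one sex and more uneven splits.** With all seven categories populated, rates of 2 to 5% give 6.3 to 11.3% within one sex, and p<0.001 about 7 to 37 times too often; one run reached 39 times. At full N, a 2/8/41 split at a 2% rate reached 46 times. There is no natural ceiling.

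**Step 5: the remedies.** A permutation (exact) chi-square on the 5/10/37 table at outcome rates of 2% and 5% rejects 5.1% and 4.9% at nominal 5%, and 0.10% and 0.12% at nominal 0.1%. Merging the three early categories gives the same table as the last row of Step 3. Over all runs its size is about 4.9 to 5.6%, but p<0.001 remains about 1.2 to 4 times too frequent.

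**The case against.** The strongest reply is that no conclusion rests on these tests. They are unadjusted first comparisons. The adjusted regressions and mixed models follow, the lowest-risk exposure is derived from the logistic models, and the hypotheses on optimal age and frequency concern that average probability. Sex-stratified results are reported only if a regression interaction is significant. All of this stands, and it limits the harm. It does not make the chi-square p-values correct, and they remain a stated analysis.

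A second reply is that the youngest category may be empty. The food surveys begin at 2 months and ask about the past 7 days, so introduction before 2 months may hardly be recorded. This also stands: the upper part of the 6 to 10.6% range needs a populated <2 m cell, which the documents do not show. With that cell empty the 5% level is only mildly exceeded, although p<0.001 is still about 3 to 8 times too frequent for rates of 2.3 to 5% while 2-3 m is populated.

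A reader might infer that every binary outcome has a false-positive rate of 6 to 10%. The documents do not support this. Split and outcome rates are assumptions, and for outcomes near 10% the full-N size is about 5 to 6.5%. Metabolic and cognitive measures are described only for Project Viva, whose introduction-age distribution is not given, so nothing can be shown there. Nor is the 0.05 under Statistical Power a claimed size for these tests; it is an input to the power calculation.

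**Conclusion.** The point holds in limited form. For the rarer IFPS II outcomes, the plan's own 1.7% and 3,033 put the smallest early cell below one expected event if all seven categories are populated, and the stated test is then anti-conservative.

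At full N and rates of 2.3 to 5%, a nominal 5% test rejects about 6 to 10.6% with all categories populated, about 5.4 to 7.5% with <2 m empty, and about 5% if all early infants are at 4-5 m. The more serious distortion is in very small p-values: p<0.001 is roughly 3 to 12 times too frequent under most splits, about twice if all early infants are at 4-5 m, and up to about 40 times within one sex or under more uneven splits.

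The expected-count bound needs no assumption about the split; the rejection rates do, and both rest on nominal outcome rates. It would be wrong to infer that the adjusted results or the lowest-risk analysis are compromised by this. It is a minor correction to a preliminary analysis.

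**What to change.** In Data analysis, Aim 1, add one sentence: where any expected count is below 5, the chi-square p-value is replaced by a Monte Carlo exact p-value (PROC FREQ, EXACT statement with the MC option). Apply the rule in both Aims and in the sex-specific tables, so that it takes effect only where the data are sparse.

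Merging <2, 2-3 and 4-5 m into one <6 m category for the IFPS II tests is second best. It restores the 5% level but leaves some excess in the far tail, and it gives up detail before 6 months.

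The cost is one sentence and one SAS option, with no new data and no change to the regressions.
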